We will perform a randomized, controlled trial (RCT) with a 12-week delayed start control group in 224 dyads of people with memory loss (PWML) and caregivers (CGs). Our primary outcome in PWML will be self-rated quality of life (Quality of Life in Alzheimer’s Disease, QOL-AD). Secondary outcomes will include: a) self-reported emotional well-being; b) self-reported social isolation; c) self-reported mobility; and d) directly assess cognitive performance. In CGs, the primary outcome will be self-rated quality of life (SF-12). Secondary outcomes in CGs will include: a) healthy days; b) self-efficacy; c) burden; d) social isolation; e) ability to self-regulate; f) positive affect; and g) sleep quality. In addition, we will ask CGs to report sleep quality, mobility, and cognitive function for PWML. Additional exploratory outcomes will include health services utilization (hospitalizations, emergency department visits) and falls.

Interventions and Duration

Eligible dyads will be enrolled in cohorts of 16. After being screened for eligibility, consented (V0), and completing baseline assessments (V1), dyads will be randomly assigned to immediate start intervention ($n=8$ dyads/cohorts) or delayed start control ($n=8$ dyads/cohorts). A total of 14 cohorts will be enrolled to achieve our target sample size of 224 dyads. Immediate start groups will participate in the livestreaming Moving Together program from their homes for 1 hour, 2 days/week, for 12 weeks, while delayed start groups will engage in usual activities. Twelve-week follow-up assessments will be performed in both groups (V2). The immediate start group will then be invited to participate in maintenance classes on a paid basis, while the delayed start group

participates in the Moving Together program for 1 hour, 2 days /week for 12 weeks. Twenty-four-week follow-up assessments will then be performed in both groups (V3), and the delayed start group will be invited to join the maintenance classes on a paid basis.

Sample Size and Population

224 dyads of persons with memory loss and their caregivers (448 persons total).

STUDY TEAM ROSTER AND STUDY SITES

Principal Investigators:

[name], MPH

University of California, San Francisco,
[name]
[contact]
[contact]

[name], MBA

Together Senior Health, Inc.
[name]
[name]
[contact]
[contact]

Co-Investigators:

[name]

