3 STUDY DESIGN

We will perform a randomized, controlled trial (RCT) with a 12-week delayed start control group in 224 dyads (Figure 1). Dyads will be enrolled in cohorts of 16. After being screened for eligibility, consented (V0), and completing baseline assessments (V1), dyads will be randomly assigned to immediate start intervention ($n=8$ dyads/cohort) or delayed start control ($n=8$ dyads/cohort) groups. A total of 14 cohorts will be enrolled to achieve our target sample size of 224 dyads. Immediate start groups will participate in the livestreaming Moving Together program from their homes for 1 hour, 2 days/week, for 12 weeks, while delayed start groups engage in usual activities. Twelve-week follow-up assessments will be performed in both groups (V2). The immediate start group will then be invited to participate in maintenance classes on a paid basis, while the delayed start group participates in the Moving Together program for 1 hour, 2 days/week for 12 weeks. Twenty-four week follow-up assessments will then be performed in both groups (V3), and the delayed start group will be invited to join the maintenance classes on a paid basis. Those who participate in the maintenance classes will be invited to provide ongoing feedback.

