4.2 Exclusion Criteria

Any candidates meeting any of the exclusion criteria during the telephone screening will be excluded from study participation.

- Age < 18 years;
- primarily use wheel-chair inside home;
- limited life expectancy (e.g., enrolled in hospice, meta-static cancer);
- physical limitations that could affect ability to participate (e.g., difficulty sitting for 1 hour, chronic pain, vertigo);
- severe visual impairment (e.g., unable to observe instructor's movements on screen);
- severe hearing impairment (e.g., unable to hear instructor's requests);
- behavioral or psychiatric issues that could be disruptive in group setting (e.g., history of physical or verbal abuse, schizophrenia, bipolar disorder, substance abuse);
- unable to provide consent/assent;
- planning to travel for >1 week during initial 12-week study period
- current participation in another research study
- started dementia medication in past 3 months
- planning dementia medication change during next 6 months
- a fracture of back or spine including a compression fracture or hairline fracture

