5.2.3 Baseline and Follow-Up Assessments (V1, V2, V3)

All participants will complete the assessments listed below at baseline (V1), 12 weeks (V2) and 24 weeks (V3). Detailed descriptions of each measure are provided below, in section 5.3.

Persons with Memory Loss (PWML) outcome measures:

- Primary:
 - Quality of life (Quality of Life in Alzheimer's Disease Scale, QOL-AD)¹⁹
- Secondary:
 - Well-being (Neuro-QOL v1.0 Positive Affect and Well-Being Short Form)²⁰
 - Social isolation (PROMIS v2.0 social isolation scale)²¹
 - Mobility (Neuro-QOL Short Form V1.0 - Lower Extremity Function - Mobility)²⁰
 - Cognitive function (telephone Montreal Cognitive Assessment, t-MoCA)²²

Caregivers outcome measures:

- Primary:
 - SF-12²³
- Secondary:
 - Healthy Days (CDC)²⁴
 - Caregiver self-efficacy (GAIN in Alzheimer Care Instrument)²⁵
 - Caregiver burden (Zarit Burden Interview, 6-item version)²⁶
 - Caregiver social isolation (PROMIS v2.0 social isolation scale)²¹
 - Caregiver self-regulation (Abbreviated MAIA-2 self-regulation subscale)²⁷
 - Caregiver positive affect (Positive States of Mind)²⁸
 - Caregiver sleep (Symptom Checklist, 3 items)
 - PWML sleep (Symptom Checklist, 3 items)
 - PWML mobility (Neuro-QOL Short Form V1.0 - Lower Extremity Function - Mobility)²⁰
 - PWML cognitive function (Cognitive Function Instrument – Modified)

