5.2.4 Monthly Check-Ins (C1, C2, C3, C4, C5, C6)

Monthly check-ins will be performed with caregivers in both groups throughout the 24-week study period. The goals of the check-ins are to: a) assess for adverse events, including hospitalizations, emergency department visits, and falls; b) assess for co-interventions that could impact our study outcomes; and c) maintain contact and interest in the waitlist control group. Check-ins may be performed by email, telephone, text, or online survey.

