10.3 Data Analyses

We will examine distributions of all variables to assess for missingness, outlier values or skewed distributions using standard techniques (e.g., means, medians, standard deviations, ranges, tables, graphical techniques). We will assess balance between the immediate and delayed start groups by comparing baseline characteristics (e.g., means \pm SD, N [%]). If meaningful differences occur by chance, we will perform sensitivity analyses adjusting for these differences.

Our primary analytic approach will be linear mixed models (LMMs) with terms included for group, time, and group*time interaction with random intercepts and slopes. This approach will enable efficient estimation of change in primary outcomes over time while including all participants randomized (intent-to-treat) and accounting for baseline values and correlations between repeated measures over time. Milestone 1a will determine if there is a significant group*time interaction for our primary outcome of quality of life, with separate analyses performed for PWML and CGs. Milestone 1b will involve exploratory analyses to examine potential mechanisms of action. These will include using PROCESS to assess for indirect effects (mediation) and contingent effects (moderation) based on baseline characteristics of our study participants (e.g., age, sex, caregiving relationship) and changes in secondary outcomes (e.g., mobility, well-being, isolation). Exploratory analyses also will examine the impact of 'dose' (based on class attendance), and sensitivity analyses will be restricted to those with high compliance ($\geq 75\%$ class attendance). For covariates that have more than 10% missing data, we will consider using multiple imputation.

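### Section 10.3 rests Milestone 1a on a group*time interaction without naming visits, time coding or contrast; with linear time over V1 to V3, week 12, the only follow-up with an untreated control, gets no weight

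*Combined protocol and SAP*

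**What the plan says.** Section 10.3 gives the primary model as "linear mixed models (LMMs) with terms included for group, time, and group*time interaction with random intercepts and slopes". It sets the decision rule as follows: "Milestone 1a will determine if there is a significant group*time interaction for our primary outcome of quality of life". People with memory loss (PWML) and caregivers are analysed separately. The section does not say which visits enter, whether time is linear or categorical, or which contrast decides. Milestone 1a in section 1.2 and the power statement in section 10.2 name no time point either.

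Section 5.2.3 schedules quality of life at V1 (baseline), V2 (week 12) and V3 (week 24). Under section 3, controls follow usual activities until V2. After V2 the immediate arm may pay to continue, "while the delayed start group participates in the Moving Together program for 1 hour, 2 days/week for 12 weeks". V3 is measured after that.

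On the intended horizon the document points both ways. The Précis and section 3 describe a 12-week delayed-start control. Section 4.2 refers to travel "during initial 12-week study period". Section 5.3.4 sets a three-month recall period to fit the study's length. Section 5.2.4, however, says: "Monthly check-ins will be performed with caregivers in both groups throughout the 24-week study period".

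**The concern.** V2 is the only post-baseline outcome visit at which a treated arm can be compared with an untreated one. Three analyses fit the wording of section 10.3:

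1. **V1 to V3, linear time.** The interaction is a difference in slopes over 24 weeks, and the control arm is treated for the second half.
2. **V1 to V3, categorical time.** The model contains the correct group-by-V2 coefficient, but the group*time test has 2 degrees of freedom and also responds to V3.
3. **V1 and V2 only.** The fixed effect is the right one.

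The random slopes lean towards the first. With two visits and a free intercept-slope covariance, the four variance parameters (intercept, slope, covariance, residual) cannot be estimated from three variance-covariance elements. This is an inference, since the text never calls time linear.

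The readings can give different verdicts on the same data. Under the first, a programme that works in both arms is expected to look like no effect. Labelling the arms A and B for the statistician (section 6.2) hides direction but not significance, so it does not protect the choice among readings.

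**Working it through.** **Inputs from the documents.** 112 per arm, two-sided alpha 0.05, standardized effect 0.375 and 20% attrition (section 10.2); visits at weeks 0, 12 and 24 (section 5.2.3).

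**Assumptions (not in the documents).** Baseline SD is 1. The random intercept's share of baseline variance is r = 0.5 to 0.8, which is the between-visit correlation when slope variance is 0. Slope variance is s = 0 to 0.10 per 12-week unit of time. The V2 effect is 0.375 SD. Controls gain 0.375 SD by V3 unless stated otherwise.

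**Step 1: the plan's own figure.** n per arm = 2(1.960 + 0.842)²/0.375² = 111.7, so 112. Power at 112 per arm is 80.1% (normal) or 79.8% (t-test). The 224 reproduces.

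**Step 2: weight on V2 with linear time.** With visits coded 0, 1, 2, complete data and a random intercept and slope with independent residuals, each person's slope is estimated with weights (t − 1)/Σ(t − 1)² = (−1/2, 0, +1/2), whatever the random-effect variances. So

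interaction = ½ × [(V3 − V1) immediate − (V3 − V1) delayed].

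In a REML fit to simulated data, adding 1 SD to every immediate-arm V2 score left the interaction estimate unchanged at −0.0454 per 12 weeks. Only its standard error moved, from 0.055 to 0.069.

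**Step 3: variances.** Per person, the slope variance is s + (1 − r)/2 and the variance of V1-to-V2 change is s + 2(1 − r). The standard error of a between-arm difference is √(2 × variance/112). Power uses the normal approximation.

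**Step 4: power of the V1-to-V2 contrast, complete data.** Example at r = 0.5, s = 0: SE = √(2 × 1.0/112) = 0.1336; 0.375/0.1336 = 2.806; power = Φ(2.806 − 1.960) = 0.801.

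| s | r = 0.5 | 0.6 | 0.7 | 0.8 |
|---|---|---|---|---|
| 0 | 80% | 88% | 95% | 99% |
| 0.03 | 79% | 87% | 94% | 99% |
| 0.10 | 76% | 84% | 92% | 98% |

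**Step 5: the linear V1-to-V3 interaction on the same V2 effect, complete data.** The result depends on the arm difference left at V3. Example, half the gain lost, r = 0.5, s = 0: difference at V3 = 0.1875 − 0.375 = −0.1875; interaction = −0.0938; SE = √(2 × 0.25/112) = 0.0668; ratio −1.403; chance of significance in the wrong direction = Φ(1.403 − 1.960) = 0.289.

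| Course after V2 | Difference at V3 | Result over r and s |
|---|---|---|
| Gain kept, controls catch up | 0 | rejects 5% |
| Quarter of gain lost, controls catch up | −0.094 | wrong direction 9% to 20% |
| Half of gain lost, controls catch up | −0.188 | wrong direction 22% to 60% |
| Gain grows to 1.5 times, or controls gain half as much | +0.188 | favours programme 22% to 60% |
| Gain doubles, controls catch up | +0.375 | favours programme 66% to 99% |

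The half-lost range is 29% to 60% at s = 0, 26% to 49% at s = 0.03 and 22% to 35% at s = 0.10. REML fits to 300 simulated trials per cell (s = 0.10; r = 0.5 and 0.8) gave 6.7% and 3.7% when the gain was kept, and 22.0% and 35.7% when half was lost.

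**Step 6: 20% attrition.** Three patterns were tried: 20% miss V3; 10% miss both visits and a further 10% miss V3; 20% miss both. V2's weight rises to 0.007 to 0.057 at s = 0 and 0.007 to 0.091 at s = 0.10. Over all patterns:

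- gain kept, controls catch up: linear test rejects 5% to 8%, V1-to-V2 contrast 69% to 99%;
- half of gain lost: wrong direction 11% to 49%.

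**Step 7: categorical time.** If the arms differ by 0.375 SD at V3 only, with no V2 effect, the 2-df interaction test rejects 73% to 99.8% with complete data. A significant result there would say nothing about week 12.

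**The case against.** The best case against is that the harm needs a reading the text never states. A random slope describes covariance and can sit beside categorical fixed time. Most of the document points to week 12: the hypothesis compares with delayed-start controls, who are untreated only until V2; section 10.2 sizes it as a two-group t-test and mentions treatment of both arms only for Milestone 1b; and the 24-week phrase concerns check-ins. On this view the point is a clarification.

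The magnitudes are also scenario-bound. The 5% figure needs full retention and full catch-up. If half the V2 difference remains at V3, the linear test has 29% to 44% power at correlations of 0.5 to 0.7. Exactly zero weight needs complete data: at the top attrition case V2 has 0.091 against 0.455 for V3, about a fifth. The upper reversal rates need zero slope variance, although the plan specifies random slopes; with s = 0.10 and attrition the half-lost range is 11% to 28%. A correlation of 0.3 to 0.4 (s = 0, complete data) would lower the V1-to-V2 contrast to 66% to 73%.

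All of that stands as a limit on the numbers. It does not remove the gap. If week 12 is intended, the section that decides the primary hypothesis does not say so, and its random slopes fit poorly with the two-visit model that would deliver it. Categorical time still needs a named contrast. Under attrition the linear test stays at 5% to 8% in the catch-up case.

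**Conclusion.** The concern holds and should be fixed before analysis. The omission is a matter of text: no visit, coding or contrast is named for the test that decides Milestone 1a in either population. The zero weight on V2 is exact for linear time, equally spaced visits, complete data and the stated random effects. That the trial would be analysed this way is not established, only left open.

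The firmest size is the catch-up case: about 5% rejection against 76% to 99% for the V1-to-V2 contrast with complete data, and 5% to 8% against 69% to 99% with 20% attrition. It assumes a V2 effect of 0.375 SD, r of 0.5 to 0.8, s of 0 to 0.10, a kept gain and full catch-up by controls. Full catch-up is what one would expect if the programme works as well when started late, but the documents do not give the course after V2. The wrong-direction rates depend more heavily on that unknown course and are illustrations, not forecasts.

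**What to change.** State in section 10.3 that Milestone 1a is the between-arm difference in V1-to-V2 change, tested as a named group-by-V2 contrast with time as a categorical factor, in both the PWML and the caregiver analysis. Report V3 separately as secondary or descriptive, since both arms have by then been offered the programme.

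The cost is one or two sentences and the matching contrast in the model code, settled before analysis. No new data or participants are needed. The covariance structure, any alpha rule across the primary outcomes and the choice of SF-12 composite are separate matters that this change does not settle.

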1.2 Milestones

Milestone 1a: Test the hypothesis that Moving Together significantly improves self-rated quality of life compared to delayed start controls on validated measures.

Milestone 1b: Perform exploratory analyses to determine whether improvements in quality of life are correlated with ‘dose’ based on number of classes attended and to examine potential mechanisms (such as changes in mobility, well-being or social isolation).

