10.2 Sample Size and Power

To be conservative, power estimates were based on an unpaired t-test analysis with two-sided alpha=0.05. A sample size of 224 (112/group) will provide us with 80% power to detect a clinically meaningful standardized effect size of 0.375 to test Hypothesis 1a.

Assuming 20% attrition, we would have 80% power to detect a standardized effect size

of 0.395. For hypothesis 1b, we will be able to conduct exploratory analyses using the full sample of 224, since both groups will receive the intervention and will be offered the opportunity to participate in maintenance classes. Again assuming 20% attrition, a final sample of 179 will provide 80% power to detect correlation coefficients as small as 0.20.

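### Random intercepts and slopes cannot be separated on V1-V2 and may give the V2 contrast a wrong standard error over V1-V3; an unstructured covariance with a named V2 contrast avoids both

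*Combined protocol and SAP*

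**What the plan says.** Section 10.3 (Data Analyses) gives the primary approach as "linear mixed models (LMMs) with terms included for group, time, and group*time interaction with random intercepts and slopes". It then states that "Milestone 1a will determine if there is a significant group*time interaction for our primary outcome of quality of life", with PWML and caregivers analysed separately. Random intercepts and slopes are the only covariance structure named. The section does not state the time coding, the visits included, the primary contrast, any robust standard error, or what to do if the model does not converge.

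Section 5.2.3 schedules the outcomes at three equally spaced visits: baseline (V1), 12 weeks (V2) and 24 weeks (V3). Section 3 has the immediate group invited to paid maintenance classes after V2, "while the delayed start group participates in the Moving Together program for 1 hour, 2 days/week for 12 weeks". Section 1.2 words Milestone 1a as "Test the hypothesis that Moving Together significantly improves self-rated quality of life compared to delayed start controls on validated measures". Only V1 and V2 compare treated with untreated dyads.

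Section 10.2 sizes the trial without the mixed model: "power estimates were based on an unpaired t-test analysis with two-sided alpha=0.05".

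**The concern.** The standard error and p-value for Milestone 1a depend on the covariance model. An analyst who wants the randomised comparison can take one of two routes, and the stated structure fits neither well.

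- **V1 and V2 only.** A random intercept, a random slope, their covariance and a residual are more parameters than two visits can separate. The software may fail or warn, and the plan names no alternative. The model for the primary test would then be chosen after the data are seen.
- **V1 to V3 with a contrast at V2.** The model can be estimated, but it treats each person's path as a straight line plus independent noise of constant variance. The two 12-week changes must then have the same variance. The precision of the V2 effect is drawn partly from V2-V3, when the controls are taking classes. If the two intervals differ in variance, the test of Milestone 1a is too liberal or too conservative, and nothing in the output need show it.

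**Working it through.** **The plan's own figure.** Inputs from section 10.2: d = 0.375, two-sided alpha 0.05, power 80%. n per arm = 2 × (1.960 + 0.842)² / 0.375² = 111.6, so 112 per arm and 224 in total. Power at 112 per arm is 0.801 (normal) or 0.798 (t). The figure reproduces. It rests on a t-test, so this point does not change it.

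**Two visits.** Code time 0 and 1. Let a = intercept variance, c = covariance, b = slope variance, s² = residual variance. Then:

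- Var(V1) = a + s²
- Cov(V1,V2) = a + c
- Var(V2) = a + 2c + b + s²

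That is three equations for four unknowns (rank 3). For example, with unit variances and correlation 0.6 (assumed), both of these sets give variances of 1 and a covariance of 0.6:

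- a = 0.90, c = -0.30, b = 0.60, s² = 0.10
- a = 0.70, c = -0.10, b = 0.20, s² = 0.30

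On one simulated data set, three optimisers reached the same log-likelihood (-445.4012) with residual variances of 0.284, 0.287 and 0.246. The standard error of the V2 contrast was 0.1212 each time. The decomposition is arbitrary, but the implied 2×2 matrix is saturated and the inference is unaffected.

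**Three visits, visit categorical, V2 contrast.** The model now has four parameters against six distinct elements (rank 4), so it is identified with two restrictions. Write S = (V3 - V1)/2 and D = V1 - 2·V2 + V3. Then V2 - V1 = S - D/2 and V3 - V2 = S + D/2. The model makes S and D uncorrelated. With complete data and a fitted slope variance above zero, likelihood matches Var(S) and Var(D) to their true values. Hence

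model Var(V2-V1) = Var(S) + Var(D)/4 = average of the two true interval variances.

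With unit variances, Var(V2-V1) = 2(1 - r12) and Var(V3-V2) = 2(1 - r23). The SE ratio is √(model/true), and type I error = 2[1 - Φ(1.96 × ratio)]. All correlations are assumptions.

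| r12 / r23 / r13 | true Var(V2-V1) | true Var(V3-V2) | model | SE ratio | type I |
|---|---|---|---|---|---|
| 0.5 / 0.7 / 0.5 | 1.00 | 0.60 | 0.80 | 0.894 | 8.0% |
| 0.4 / 0.7 / 0.4 | 1.20 | 0.60 | 0.90 | 0.866 | 9.0% |
| 0.55 / 0.65 / 0.5 | 0.90 | 0.70 | 0.80 | 0.943 | 6.5% |
| 0.65 / 0.55 / 0.5 | 0.70 | 0.90 | 0.80 | 1.069 | 3.6% |
| 0.7 / 0.5 / 0.5 | 0.60 | 1.00 | 0.80 | 1.155 | 2.4% |
| compound symmetry 0.6 | 0.80 | 0.80 | 0.80 | 1.000 | 5.0% |
| AR(1) 0.6 | 0.80 | 0.80 | 0.80 | 1.000 | 5.0% |

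A wider gap takes it further: 0.75 / 0.5 / 0.5 gives 1.6%.

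**Power in the conservative case** (0.7 / 0.5 / 0.5, 112 per arm, d = 0.375). The true SE is √(2 × 0.60/112) = 0.1035, and 0.375/0.1035 = 3.62. With the correct SE, power is Φ(3.62 - 1.96) = 95%. With the model SE it is Φ(3.62 - 1.96 × 1.155) = 91%.

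**Finite-sample check** (112 per arm, 1,000 runs). Type I error was 8.6% against 6.3% with an unstructured covariance (0.5 / 0.7 / 0.5), and 3.0% against 5.9% (0.7 / 0.5 / 0.5). Simulation error at 5% is √(0.05 × 0.95/1000) = 0.7 percentage points.

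**Linear time.** The group*time term then rests on S alone, whose variance the model reproduces exactly, so the SE ratio is 1.000.

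**The case against.** Four objections carry weight.

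- **A reader might infer that the primary model cannot be fitted to the randomised comparison, or that its result would be invalid.** The documents do not support that. Section 10.3 never says the model is limited to V1-V2. If it were, only the variance components would be arbitrary; the V2 contrast and its standard error would stand. What remains is possible non-convergence with no stated fallback.
- **The three-visit distortion needs a model the plan does not spell out:** categorical visits and a V2 contrast alongside a linear random slope. If time is read as linear, the SE error is absent. This stands. But the test is then a 24-week slope difference that includes the controls' own class period, not the V2 effect Milestone 1a asks about.
- **A reader might infer that the change of condition at V2 itself inflates type I error to 8% or 9%.** It does not. The arms mirror each other: variable response to classes adds variance to the first interval in one arm and to the second in the other. A persisting random response on compound symmetry gave a ratio of 1.00. Letting the response fade (assumed correlation 0.5 or 0.7, response variance 0.1 to 0.5, fading 0 to 100%) gave ratios between 1.00 and 1.05, never below 1. The larger errors need a difference between intervals that the two arms share. The documents neither show nor exclude one.
- **The practical size may be modest.** In the conservative case power is 91% rather than 95%, both above the planned 80%.

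These points limit the size of the problem. They do not give a reason to keep a restriction that the V2 test does not need.

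**Conclusion.** The point holds in a limited form. On V1-V2 alone, the stated random effects are not separable (four parameters, three moments). This is exact and needs no assumed figure, but it leaves the V2 inference intact and matters only through convergence and an unplanned choice of model. On V1-V3 with a V2 contrast, the standard error is tied to the average of the two interval variances. It is too small or too large when they differ: about 2.4% to 9% type I error under the main assumed correlations, and 5% under compound symmetry or AR(1).

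The documents give no between-visit correlations, so the size and even the direction are unknown. It would go too far to say that the plan's type I error is inflated. What can be said is that the stated structure does not guarantee the nominal level for the V2 contrast, whereas an unstructured covariance does in large samples. The sample size of 224 is unaffected. The change should be made because it is almost free and concerns the primary test in both PWML and caregivers.

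**What to change.** In section 10.3, replace the words on random intercepts and slopes by: *with visit as a categorical factor and an unstructured within-person covariance across V1-V3, fitted by REML with Kenward-Roger degrees of freedom; Milestone 1a is the 1-df group-by-visit contrast at V2 (change from V1 to V2).* Apply this to both the PWML and the caregiver primary outcome.

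The contrast must be named. With categorical visits, an unqualified group*time test has 2 df and includes V3, after the controls have had the classes.

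Add a fallback: *if the three-visit model does not converge, fit the unstructured model to V1 and V2 only.* That has three covariance parameters and is identified. A heterogeneous Toeplitz structure should not be the fallback. It imposes corr(V1,V2) = corr(V2,V3) and leaves type I error at 7.6%, 8.4% and 2.6% in the sets that gave 8.0%, 9.0% and 2.4%.

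The cost is a sentence or two of analysis text and two more covariance parameters (six instead of four) with 224 dyads. The loss of precision is negligible, and no visit, measure or sample size changes.

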6 RANDOMIZATION AND BLINDING

6.1 Randomization

Study participants will be enrolled in cohorts (blocks) of 16 dyads and randomly allocated to the immediate start intervention group ($n=8/\text{cohort}$) or the delayed start control group ($n=8/\text{cohort}$). The randomization sequence will be generated in advance by the data manager using a random number generator on a computer and will be stored separately and securely. Research staff will be unaware of the randomization sequence.

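### The primary mixed model estimates a separate baseline mean in each arm although V1 precedes randomisation; a common baseline mean would give a more precise 12-week estimate from the same data

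*Combined protocol and SAP*

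**What the plan says.** Section 10.3 (Data Analyses) specifies linear mixed models with "terms included for group, time, and group*time interaction with random intercepts and slopes". Milestone 1a is the test of the group-by-time interaction for quality of life, run separately for people with memory loss and for caregivers. The same section describes the approach as estimating change "while including all participants randomized (intent-to-treat) and accounting for baseline values and correlations between repeated measures over time". On baseline differences between arms it adds only: "If meaningful differences occur by chance, we will perform sensitivity analyses adjusting for these differences".

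Section 3 (Study Design) gives the order of events: after "completing baseline assessments (V1), dyads will be randomly assigned to immediate start intervention" or delayed start control. V2 at 12 weeks is measured in both groups before the controls take any classes. Between V2 and V3 the immediate group may join paid maintenance classes, "while the delayed start group participates in the Moving Together program for 1 hour, 2 days/week for 12 weeks".

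No section constrains the baseline means to be equal or enters the baseline outcome as a covariate in the primary model. Section 10.3 does not say whether time is categorical or linear, or whether V3 contributes to the Milestone 1a test.

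**The concern.** With V1 as one of the repeated outcomes and a free group term, the model spends information on estimating a baseline difference that randomisation has already set to zero in expectation. The interaction removes the observed baseline difference by subtraction, so the estimate is unbiased and the test valid. But full subtraction over-corrects when the correlation between visits is below 1. The sensitivity adjustment for chance imbalance does not change the primary model.

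What is at stake is precision in both primary analyses. Section 10.2 (Sample Size and Power) adds a second aspect: "To be conservative, power estimates were based on an unpaired t-test analysis". If the planned effect of 0.375 is in SDs of the outcome score, which the documents do not say, the t-test is conservative for the planned contrast only when the V1-to-V2 correlation is about 0.5 or more. If 0.375 is in SDs of change, this second aspect does not arise.

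**Working it through.** **Inputs from the documents.** 112 dyads per group, two-sided alpha 0.05, effects of 0.375 and (with attrition) 0.395, 20% attrition leaving 179 dyads (all 10.2); 14 cohorts, hence 14 immediate-start classes (3).

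**Assumed.** V1-to-V2 correlation rho of 0.3 to 0.8; equal SDs at V1 and V2 (variances below are in units of the squared SD); visit categorical; dyads independent; V2 missing completely at random. All n = 112 per arm have V1, and m = 179/2 = 89.5 per arm have V2.

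**The plan's own figure.** n per group = 2(1.96 + 0.8416)²/0.375² = 111.6, so 112. The exact t-test power is 79.8%, so the stated 80% reproduces.

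**Variance of the V2 contrast.**
- Complete data: separate baselines 4(1 − rho)/n; common baseline 2(1 − rho²)/n. Their ratio is (1 + rho)/2, below 1 for every rho below 1.
- With attrition: separate 2[(1 − rho²)/m + (1 − rho)²/n]; common 2(1 − rho²)/m.

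Example, rho = 0.5 with attrition: separate = 2[0.75/89.5 + 0.25/112] = 0.02122; common = 2 × 0.75/89.5 = 0.01676. Ratio 0.790, a 21.0% reduction in variance; the square root is 0.889, an 11.1% reduction in standard error.

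| rho | Complete: variance reduction | Attrition: separate | Attrition: common | Variance reduction | SE reduction |
|---|---|---|---|---|---|
| 0.3 | 35.0% | 0.02909 | 0.02033 | 30.1% | 16.4% |
| 0.5 | 25.0% | 0.02122 | 0.01676 | 21.0% | 11.1% |
| 0.7 | 15.0% | 0.01300 | 0.01140 | 12.4% | 6.4% |
| 0.8 | 10.0% | 0.00876 | 0.00804 | 8.2% | 4.2% |

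Generalised least squares with V3 added (categorical time, all dropout before V2) gives the same reductions. Simulation with the slope on baseline estimated (20,000 trials per value) gives 29.8%, 21.0%, 11.4% and 7.3%.

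**Power, only if the effect is in outcome SDs (noncentral t).**

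| rho | 0.375, complete: separate vs common | 0.395, attrition: separate vs common |
|---|---|---|
| 0.3 | 66% vs 83% | 63% vs 79% |
| 0.5 | 80% vs 90% | 77% vs 86% |
| 0.7 | 95% vs 98% | 93% vs 96% |

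**Where the t-test stops being conservative.** An unpaired t-test at V2 has variance 2/n (complete) or 2/m (attrition). Complete data: 4(1 − rho)/n = 2/n gives rho = 0.50. With attrition: rho/(1 − rho) = √(m/n) = √(89.5/112) = 0.894 gives rho = 0.47. Below these values the planned contrast is less precise than the t-test. The common-baseline contrast never is, since its variance ratio to the t-test is 1 − rho².

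**Sensitivity to class clustering.** Allocation is by cohort ("Study participants will be enrolled in cohorts (blocks) of 16 dyads and randomly allocated to the immediate start intervention group"), and the immediate arm is taught in classes. Letting class-level variance be a share (icc) of the outcome variance in the immediate arm at V2 adds icc/14 to both variances. At assumed shares of 1% to 5%, the reductions with attrition are 29–27%, 20–18%, 12–10% and 7.5–6% at the four rho values.

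**Sensitivity to linear time.** Times 0, 1, 2; V1 variance 1; random-intercept variance 0.3 to 0.8; slope variance 0.02 to 0.10; same attrition. With intercept and slope uncorrelated, the reduction in slope-contrast variance runs from 33% down to 4%. With an assumed intercept–slope correlation of −0.3 or +0.3, the range widens to about 38% down to near 0%.

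**The case against.** The strongest reply is that nothing is broken. Group, time and their interaction form a standard specification, and a constrained baseline is an efficiency choice. The size of the gain rests on a correlation that the documents do not supply for either the QOL-AD or the SF-12, and nothing in them favours 0.5 over 0.8. That stands, and it is why a range is shown and the gain is called small at 0.7 or more. The direction does not depend on the correlation.

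A second reply is that random slopes over three visits suggest linear time as readily as categorical visits, so the V2 figures may not describe the model the authors intend. This also stands in part. Under linear time the gain can be larger or can nearly vanish, but it was not negative in any case examined.

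Third, the remedy also names V2 as the tested contrast, which is a separate question from baseline handling and possibly a more important one. That is fair. The two are stated together because the same sentence must settle both, and the precision figures apply to baseline handling alone.

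Finally, section 10.2 says: "Assuming 20% attrition, we would have 80% power to detect a standardized effect size" of 0.395. With 89.5 per arm the unpaired t-test has about 75% power at that effect. This shortfall is unrelated to baseline handling and is no evidence for this point.

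**Conclusion.** The point holds as an efficiency improvement, not as an error of validity. Equal true baseline means follow from the order of V1 and randomisation, yet the primary model does not use that fact. Under the stated assumptions the variance of the 12-week contrast could fall by 8% to 30% for rho between 0.8 and 0.3 with 20% attrition. The gain is material at about 0.5 or below and modest above 0.7. Class clustering of up to 5% trims it slightly. Linear time coding makes it more uncertain, from about 38% to almost nothing. The change should be made because it costs so little. Confidence is medium because neither the correlation nor the time coding is stated.

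**What to change.** Rewrite the model sentence in 10.3 as a constrained longitudinal model:

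- visit (V1, V2, V3) as a categorical factor;
- one common baseline mean, that is, no group main effect;
- group-by-visit terms at V2 and V3, with the V2 term named as the Milestone 1a test, since controls have not yet taken classes at that visit;
- an unstructured within-person covariance, or an explicit statement of the random-effects structure retained;
- all randomised dyads kept in the model, including those with V1 only.

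The same model can serve the secondary scales. Section 10.2 should also say whether 0.375 is in SDs of the outcome or of change.

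The cost is a protocol amendment to the analysis text, to be fixed before the statistician is unblinded. No visit, measure or participant is added.
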